2.6 REGISTRY SIZE

The estimated sample size requirement is based on both primary safety endpoints: a noninferiority comparison of the overall SAE free-rate to 92.5% at 5 years, excluding those SAEs listed in Table 4, and a non-powered, superiority comparison for those individual lead-related SAE to 1% at 5 years. The sample size for primary safety endpoint 1 was calculated based on the following assumptions:

Assumptions for primary safety endpoint 1

- Study Design: nonrandomized registry
- Type I error (alpha): 0.05 (one-sided for noninferiority)
- Statistical power: 80%
- Noninferiority delta: 5%
- Estimated SAE-Free Rate at 5 years: 92.5% for Corox BP LV Leads

For primary safety endpoint 1, a total of 240 evaluable subjects implanted with Corox BP LV leads would be required to demonstrate the noninferiority within 5% of a SAE free-rate of 92.5%. Assuming a 50% loss to follow-up rate over 5 years of follow-up, a total of 480 (240/0.5) subjects would be required to evaluate primary safety endpoint 1. Enrollment will seek to achieve 240 evaluable subjects for each of the Corox BP LV leads.

Assumptions for primary safety endpoint 2

- Estimated individual SAE rate at 5 years: 0.4%
- Allowable two-sided, upper 95% confidence bound: 1%

For primary safety endpoint 2, a total of 1000 subjects would be required to demonstrate a two-sided, upper 95% confidence bound of 1%, assuming an expected individual SAE rate of 0.4% (no more than 4 patients with an SAE out of 1000). Assuming a 50% loss to follow-up rate over 5 years (10% per year), a total of 2000 (1000/0.5) enrolled patients would be required for evaluation of primary safety endpoint 2.

The required sample sizes for the two primary safety endpoints are summarized in Table 5.

Table 5: Primary Safety Endpoints Sample Sizes

	Primary Safety Endpoint 1: Overall SAE free-rate	Primary Safety Endpoint 2: Individual SAE rates
Sample Size of Evaluable Patients	240	1000
Total with 50% Loss to Follow-Up over 5 years	480	2000

Due to the addition of the Corox OTW-L BP in the study, the total sample size was increased to 2500 to allow for sufficient enrollment of patients with this lead.

Study attrition

For the sample size calculation, a maximum loss to follow-up of 10% per year (50% over 5 years) was assumed. The loss to follow-up rate encompasses all causes for subjects to be exited from the study, including subject death, device explants, patient directed withdrawals, physician directed withdrawals, and loss of contact with the subject. BIOTRONIK will make every effort to limit the loss to follow-up, for reasons other than subject death and device explants unrelated to device design or performance, to less than 20% of the total registry enrollment cohort.

Minimum cohort size

The pre-specified secondary analysis will be conducted as an ad hoc analysis, meaning no testable hypothesis is being stated. Therefore, the minimal cohort size to analyze each lead model is based on an assumption of an equal 1/3 distribution of each lead model being enrolled in the CELESTIAL Registry. For the evaluation of the Corox OTW-L BP lead, a minimum of 600 evaluable subjects will be necessary.

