H₀: The serious adverse event-free rate (SAEFR) for the Corox BP LV Leads at 5 years post-enrollment is inferior to 92.5%

$$SAEFR + \delta \leq 92.5\%$$

H_a: The serious adverse event-free rate (SAEFR) for the Corox BP LV Leads at 5 year post-enrollment is not inferior to 92.5%

$$SAEFR + \delta > 92.5\%$$

CELESTIAL REGISTRY PROTOCOL

Where, (δ) is the clinically significant difference for establishing noninferiority. A rejection of the null hypothesis would indicate that the serious adverse event-free rate is not inferior to 92.5% within (δ).

2.3 PRIMARY ENDPOINT 2: SAFETY OF COROX BP LV LEADS – INDIVIDUAL COMPLICATION RATES

Each of the individual types of serious adverse events contributing to primary safety endpoint 1 will be evaluated separately in the following superiority hypotheses:

H_0 : The individual serious adverse event rate (SAEIndividual) for a given type of SAE for the Corox BP LV Leads at 5 years post-enrollment is equal to 1%

$$\text{SAEIndividual} = 1\%$$

H_a : The individual serious adverse event rate (SAEIndividual) for a given type of SAE for the Corox BP LV Leads at 5 years post-enrollment is not equal to 1%

$$\text{SAEIndividual} \neq 1\%$$

If the two-sided, 95% upper confidence bound is no more than 1% for individual serious adverse events, then the null hypothesis will be rejected for that SAE type.

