2.7 DATA ANALYSIS

For both primary safety endpoints 1 and 2, pooling of data from the Corox OTW BP, Corox OTW-S BP, and Corox OTW-L BP LV leads will be justified as part of the final data analysis. The differences in outcomes for the Corox OTW BP, Corox OTW-S BP, and Corox OTW-L BP LV leads will be tested using an exact, Chi-square test. If no evidence is found of differences between the Corox OTW BP, Corox OTW-S BP, and Corox OTW-L BP LV leads ($p > 0.05$), then the results will be considered poolable for purposes of testing the protocol hypotheses associated with the two primary endpoints. If evidence of differences is found for a given endpoint, then the hypotheses for that endpoint will additionally be tested separately for each LV lead.

CELESTIAL REGISTRY PROTOCOL

Primary safety endpoint 1 will be evaluated by performing an exact, noninferiority test comparing a binomial proportion (overall SAE free-rate at 5 years) to 92.5%, with a noninferiority delta of 5%. Equivalently, the upper, one-sided 95% confidence bound for the absolute difference between the overall SAE free-rate and 92.5% must not exceed 5%.

The evaluation of primary safety endpoint 2 will be based on the exact, two-sided 95% confidence interval for the observed, individual SAE rates at 5 years. The upper bound of these 95% confidence intervals must be less than 1%.

The secondary endpoint of successful biventricular pacing will be summarized as a success rate at each of the scheduled CELESTIAL follow-up visits through 5 years post-enrollment, together with the associated exact, 95% confidence intervals.

The secondary endpoint of other SAEs at 5 years, which were excluded from the primary safety analyses (listed in Table 5), will also be summarized as SAE rates together with their associated exact, 95% confidence intervals.

The secondary endpoints of pacing threshold and impedance measurements for the Corox BP LV leads will be summarized at scheduled visits where they were evaluated, using standard measures, including means, standard deviations, medians, minimums, and maximums.

The secondary endpoint for overall incidence of serious adverse events that meet the primary endpoint 1 criteria will be evaluated separately for each Corox BP lead model using the criteria established for primary safety endpoint 1 and 2.

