## 1.1 SAMPLE SIZE AND POWER

The estimated sample size requirement is based on both primary safety endpoints: a noninferiority comparison of the overall serious adverse event (SAE) free-rate to 92.5% at 5 years, excluding those SAEs listed in Protocol Table 4, and a non-powered, superiority comparison for those individual lead-related SAE to 1% at 5 years. The sample size for primary safety endpoint 1 was calculated based on the following assumptions:

### Assumptions for primary safety endpoint 1

- Study Design: nonrandomized registry
- Type I error (alpha): 0.05 (one-sided for noninferiority)
- Statistical power: 80%
- Noninferiority delta: 5%
- Estimated SAE-Free Rate at 5 years: 92.5% for Corox BP LV Leads

For primary safety endpoint 1, a total of 240 evaluable subjects implanted with Corox BP LV leads would be required to demonstrate the noninferiority within 5% of a SAE free-rate of 92.5%. Assuming a 50% loss to follow-up rate over 5 years of follow-up, a total of 480 (240/0.5) subjects would be required to evaluate primary safety endpoint 1. Enrollment will seek to achieve 240 evaluable subjects for each of the Corox BP LV leads.

### Assumptions for primary safety endpoint 2

- Estimated individual SAE rate at 5 years: 0.4%
- Allowable two-sided, upper 95% confidence bound: 1%

For primary safety endpoint 2, a total of 1000 subjects would be required to demonstrate a two-sided, upper 95% confidence bound of 1%, assuming an expected individual SAE rate of 0.4% (no more than 4 patients with an SAE out of 1000). Assuming a 50% loss to follow-up rate over 5 years (10% per year), a total of 2000 (1000/0.5) enrolled patients would be required for evaluation of primary safety endpoint 2.

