### 5.2 PRIMARY ENDPOINT 2: SAFETY OF COROX BP LV LEADS PACING – INDIVIDUAL COMPLICATION RATES

Primary endpoint 2 will be evaluated based on the exact, two-sided 95% confidence interval for the observed, individual serious adverse event rates at 5 years. The upper bound of these 95% confidence intervals must be less than 1%. This endpoint will be evaluated using the subject population defined in section 3.2 Primary Endpoint Per-Protocol (PP) Analysis Population.

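### The endpoint 2 sample-size statement allows 4 events in 1000, but the exact two-sided 95% upper bound for 4/1000 is 1.021%, so at most 3 events pass

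*Protocol*

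**What the plan says.** Protocol 2.6 sets two assumptions for primary endpoint 2: an individual SAE rate of 0.4% at 5 years, and a limit stated as "Allowable two-sided, upper 95% confidence bound: 1"%. From these it takes 1000 evaluable subjects, "assuming an expected individual SAE rate of 0.4% (no more than 4 patients with an SAE out of 1000", and doubles this to 2000 enrolled for 50% loss. SAP 1.1 repeats the calculation: "a total of 1000 subjects would be required to demonstrate a two-sided, upper 95% confidence bound of 1"%, with the same allowance of 4 events.

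The method is fixed in the analysis sections. SAP 5.2 bases the endpoint on "the exact, two-sided 95% confidence interval for the observed, individual serious adverse event rates at 5 years", and Protocol 2.7 prescribes the same exact two-sided interval.

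The pass mark is worded in two ways. Protocol 2.7 says "The upper bound of these 95% confidence intervals must be less than 1"%, and SAP 5.2 agrees. Protocol 2.3 and SAP 2.2 reject the null hypothesis "If the two-sided, 95% upper confidence bound is no more than 1% for individual serious adverse events".

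Three other statements bear on the size of the point. Both documents call the endpoint 2 comparison non-powered. Protocol 2.6 says of attrition that "a maximum loss to follow-up of 10% per year (50% over 5 years) was assumed". It also says that, because the OTW-L lead was added, "the total sample size was increased to 2500 to allow for sufficient enrollment of patients with this lead". The sample-size section of the SAP does not mention 2500.

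**The concern.** The sentence that pairs 4 events with 1000 subjects is the only basis given for the endpoint 2 sample size. It feeds the endpoint 2 column of Table 5 and matches the minimum of 2000 patients in Protocol section 2. It tells the reader that an observed rate equal to the planning rate, 4 in 1000, will meet the 1% limit. If the prescribed interval does not give that result, the documents misstate which outcome satisfies a primary safety criterion, and they make the criterion look easier to meet at 1000 subjects than it is.

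**Working it through.** **Inputs.** n = 1000 evaluable, x = 4 events, planning rate 0.4%, limit 1%, loss 50% (Protocol 2.6, SAP 1.1). Exact two-sided 95% interval (Protocol 2.7, SAP 5.2). 2500 enrolled (Protocol 2.6).

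**1. The plan's own figures.** 4/1000 = 0.4% and 1000/0.5 = 2000, so these agree with each other. The sizing sentence does not say how the bound of 1% was obtained from 4/1000.

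**2. The bound under the prescribed method.** The exact (Clopper-Pearson) two-sided 95% upper limit is the 97.5% quantile of Beta(x+1, n−x). For x = 4 and n = 1000 this is the 97.5% quantile of Beta(5, 996) = 1.021%. The full interval is 0.109% to 1.021%.

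**3. Check by the binomial tail.** The upper limit is below 1% only if P(X ≤ x | n, 1%) is below 0.025.
- P(X ≤ 3 | 1000, 1%) = 0.0100727, so 3 events pass.
- P(X = 4 | 1000, 1%) = 0.0186137.
- P(X ≤ 4 | 1000, 1%) = 0.0100727 + 0.0186137 = 0.0286864. This exceeds 0.025, so 4 events fail.

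**4. What passes.**

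| Evaluable n | Events | Exact upper bound | Result |
|---|---|---|---|
| 1000 | 3 | 0.874% | pass |
| 1000 | 4 | 1.021% | fail |
| 1021 | 4 | 1.00003% | fail |
| 1022 | 4 | 0.99906% | pass |
| 1250 | 5 | 0.931% | pass |
| 1250 | 6 | 1.042% | fail |

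The result at 4/1000 is the same under either wording of the pass mark, because 1.021% is above 1%.

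**5. Chance of passing at a true rate of 0.4%.**
- n = 1000, expected events 1000 × 0.004 = 4.0. With at most 3 events allowed the chance is 43.3%. With the stated allowance of 4 it would have been 62.9%.
- n = 1022, expected events 4.09. With at most 4 allowed it is 61.2%.
- n = 1250, expected events 5.0. With at most 5 allowed it is 61.6%.

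**6. Does another interval rescue 4/1000?** Upper limits below 1% come from the one-sided 95% exact bound (0.913%), mid-P (0.962%), Jeffreys (0.948%) and Wald (0.791%). The documents name none of these for endpoint 2. The Wilson limit is 1.024%. The Sterne and Blaker exact tests of 1% both give p = 0.055, so other exact two-sided methods do not exclude 1% either.

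**7. Size of the gap.** 1022 − 1000 = 22 evaluable subjects (2.2%), or 1022/0.5 − 2000 = 44 enrolled. From 2500 enrolled, 50% loss leaves 2500 × 0.5 = 1250 evaluable. Fewer than 1022 would remain only if loss exceeded 1 − 1022/2500 = 59.1%.

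**The case against.** The strongest reply is that this is close to rounding. The bound of 1.021% rounds to 1%, and 1000 lies within 3% of 1022. The comparison is declared non-powered, so no power claim is falsified. The word exact appears in the analysis sections and not in the sizing sentence, and 2500 enrolled more than covers the gap.

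Most of this stands as a limit on the consequence, but it does not make the sentence true. The plan gives an integer allowance against a fixed threshold, and under that threshold 4 of 1000 fails. The analysis sections leave no choice of interval. Enrolment rose to 2500 to bring in enough patients with the OTW-L lead, and the SAP still shows only 1000 and 2000 for this endpoint.

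A reader might infer something stronger: that the registry is too small, or that a conclusion would change. The documents do not support either. The verdict for each SAE type comes from the exact interval on the observed data, so 4 events in 1000 to 1021 evaluable subjects would fail whatever the planning sentence says. At the assumed loss the Protocol's enrolment leaves about 1250 evaluable. That figure does depend on the 50%, which is a planning assumption and not a guarantee; Protocol 4.3 itself warns that retention may be difficult.

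**Conclusion.** The point holds and is minor. The stated pairing of 4 events with 1000 evaluable subjects does not meet the 1% limit under the exact two-sided interval that both documents prescribe (1.021%). The correct allowance at 1000 is 3 events (0.874%), one fewer than the number expected at the planning rate. At that rate the chance of passing for a given SAE type is about 43%, against about 63% under the stated allowance.

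The effect is confined to the planning basis and to what a reader expects to pass. The final test is unaffected.

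This rests on the Clopper-Pearson form of the exact interval, a binomial count among evaluable subjects, and, for the 1250 figure, 50% loss from 2500 enrolled.

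**What to change.** Keep 1000 evaluable and 2000 enrolled, which agree with Table 5 and with the minimum in Protocol section 2. In Protocol 2.6 and SAP 1.1, replace the allowance with: *at most 3 patients with an event of that type among 1000 evaluable (exact two-sided 95% upper bound 0.874%); at a true rate of 0.4% the chance of meeting this is about 43%.* Then add: *with 2500 enrolled and the assumed 50% loss, about 1250 are evaluable and up to 5 events (0.4%) pass (upper bound 0.931%; chance about 62%).*

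The alternative is to keep 4 events and move to 1022 evaluable and 2044 enrolled. It needs more edits: the 1000/0.5 sentence in both documents, the endpoint 2 column of Table 5, and the 2000 minimum in Protocol section 2 must all change. It would still allow slightly fewer events (4) than the 4.09 expected at 0.4%.

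The first option costs a short text correction in each document. Enrolment, success rule and analysis do not change.

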3. PROTOCOL REQUIREMENTS

3.1 PATIENT POPULATION

This post approval registry will include a minimum of 2500 patients from up to 100 centers. The collection of data will continue for five years for each enrolled subject.

The investigator is responsible for screening all potential patients and selecting those who are appropriate for registry inclusion. The patients selected for participation should be from the investigator's general patient population according to the inclusion and exclusion criteria described below. Patients declining participation will be documented on a screen failure log describing the primary reason.

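### Protocol 2.6 calls for at least 600 evaluable Corox OTW-L BP subjects, but its own planning figures deliver about 417 to 479, and the gap is not reconciled

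*Protocol*

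**What the plan says.** The minimum-cohort paragraph of Protocol 2.6 (Registry Size) describes the by-model secondary analysis as ad hoc, with no hypothesis attached. It then says that "the minimal cohort size to analyze each lead model is based on an assumption of an equal 1/3 distribution of each lead model" being enrolled, and the next sentence is "For the evaluation of the Corox OTW-L BP lead, a minimum of 600 evaluable subjects will be necessary". No arithmetic follows.

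The other inputs are in the same section or close to it:

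- **Loss.** "a maximum loss to follow-up of 10% per year (50% over 5 years) was assumed", covering every reason for exit, including death and explant. SAP 5.6 repeats 50% over 5 years. A separate retention aim is to hold losses "for reasons other than subject death and device explants unrelated to device design or performance, to less than 20" percent of the enrolled cohort.
- **Enrolment.** Once OTW-L was added, "the total sample size was increased to 2500 to allow for sufficient enrollment of patients with this lead". Protocol 3.1 states it as a floor: "This post approval registry will include a minimum of 2500 patients from up to 100 centers".
- **Another per-lead figure.** "Enrollment will seek to achieve 240 evaluable subjects for each of the Corox BP LV leads". SAP 1.1 repeats this. The 600 appears nowhere in the SAP.
- **Who counts at 5 years.** Protocol 2.7.2 admits patients with 5 years of follow-up or an earlier SAE. SAP 3.3.3 applies the same idea to OTW-L: a primary-endpoint event, or a visit or system revision at about 5 years.

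**The concern.** The other sample-size steps in Protocol 2.6 can be followed from evaluable to enrolled: 240 becomes 480, and 1000 becomes 2000. The 600 cannot. It is worded as a necessary minimum and follows a sentence naming the one-third split, yet one third of 2500 at the planned loss falls well short of it. A reader cannot tell what loss or lead mix the 600 presupposes, or whether the OTW-L commitment is 600 or 240.

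The OTW-L cohort size has some bearing on inference. SAP 5.3.5 specifies an exact noninferiority test with a p-value for each model, and SAP 5.3.6 compares each model's upper bound with 1%. If poolability fails, Protocol 2.7 and SAP 4 also test the primary hypotheses by lead.

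**Working it through.** **Inputs.** Enrolment 2500, share 1/3, loss 50% over 5 years (Protocol 2.6). SAE rate 7.5%, from the assumed 92.5% SAE-free rate (Protocol 2.2 and 2.6). Noninferiority limit 92.5% − 5% = 87.5%, one-sided alpha 0.05. Individual SAE rate 0.4%, with the upper bound to be below 1%.

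**1. The plan's other figures reproduce.** 240/0.5 = 480 and 1000/0.5 = 2000. Exact power at n = 240 (true 92.5% against 87.5%) is 80.7%, matching the stated 80%. So in this section evaluable means the number left after loss.

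**2. The OTW-L yield at the planning figures.**

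- Enrolled: 2500/3 = 833.3
- Completers only: 833.3 × 0.5 = 416.7, about 417
- Plus early-SAE patients, SAE independent of loss: 833.3 × (0.5 + 0.5 × 0.075) = 447.9, about 448
- Plus early-SAE patients, all of them otherwise lost: 833.3 × (0.5 + 0.075) = 479.2, about 479

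Against 600, 417 is 31% short and 479 is 20% short.

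**3. Sensitivity to compounding.** The documents equate 10% per year with 50%. If 10% were compounded, which they do not say, retention would be 0.9^5 = 0.590. That gives 492 completers and at most 492.1 + 62.5 = 554.6, about 555, or 8% short.

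**4. What 600 would require.**

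| Who counts as evaluable | Largest total loss at 833 enrolled | OTW-L enrolled needed at 50% loss |
|---|---|---|
| Completers only | 1 − 600/833.3 = 28.0% | 600/0.5 = 1200 (48.0% of 2500) |
| Plus early SAE, independent of loss | 28.0/0.925 = 30.3% | 600/0.5375 = 1117 (44.7%) |
| Plus early SAE, all among the lost | 28.0 + 7.5 = 35.5% | 600/0.575 = 1044 (41.8%) |

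The retention aim of under 20% does not supply the first condition. If 20% were the total loss, the yield would be 833.3 × 0.8 = 667, but that aim leaves out deaths and unrelated explants.

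**5. The endpoint 2 rule does not yield 600 either.** The smallest n with an exact two-sided 95% upper bound below 1% is 368 for 0 events, 555 for 1 and 720 for 2.

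**6. What the difference does to the by-lead results.**

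| Evaluable | Bound, 0 events | Bound, 1 event | Bound, 2 events | P(bound < 1%) at true 0.4% | Exact power against 87.5% at true 92.5% |
|---|---|---|---|---|---|
| 417 | 0.88% | 1.33% | 1.72% | 19% | 95% |
| 479 | 0.77% | 1.16% | 1.50% | 15% | 97% |
| 600 | 0.61% | 0.93% | 1.20% | 31% | 99% |

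The power at 417 is 91% if the lower limit is taken from a two-sided 95% interval.

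**The case against.** The strongest reply is that nothing here contradicts anything else. The 50% is a ceiling on loss and the 2500 a floor on enrolment, so 417 is the yield at the planning limits, not a forecast. A requirement above that yield is a condition on recruitment and retention, not a failed sum. This stands. A reader might infer that 600 is impossible or an arithmetic error, and the documents do not support that. Nor is 479 an absolute ceiling: it holds only for a flat 50% loss.

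It can also be said that the one-third sentence concerns all models while the 600 concerns OTW-L alone, and that enrolment was raised for this lead, so a larger OTW-L share may have been intended. That is possible, but no such share is stated and the only distribution given is one third.

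A third reply is that evaluable might mean all enrolled, as SAP 3 uses for secondary endpoints 1 to 4. On that reading about 833 would be available and 600 would be met. It fits poorly with a section that treats evaluable as the number after loss: "a total of 2000 (1000/0.5) enrolled patients would be required for evaluation of primary safety endpoint 2". For the 5-year by-lead endpoints, Protocol 2.7.2 and SAP 3.3.3 already say who counts.

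Finally, the consequence is small. The secondary analysis is descriptive by the protocol's account, endpoint 2 is labelled non-powered, and 417 comfortably exceeds 240. The 19% against 31% contrast is partly discreteness: the pass probability is 22.9% at n = 368 and 21.8% at n = 719. All of this stands and limits the weight of the point.

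**Conclusion.** The point holds as an unreconciled figure, of minor severity. At 2500 enrolled, one third OTW-L and 50% loss, the plan delivers about 417 completers, or 448 to 479 if patients with an early primary-endpoint SAE count, assuming a 7.5% SAE rate. The stated minimum is 600, and the conditions under which it would be met are not given. The 240-per-lead target in both documents is met at 417 but is not related to the 600.

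A reader might go further and infer that the primary analysis is undersized. It is not: the pooled primary analysis does not depend on this number, and even by lead the 87.5% criterion keeps about 95% power at 417. The tangible difference is in the comparison with 1%, where across 417 to 479 only zero events of a given type passes, against at most one event at 600.

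**What to change.** In the minimum-cohort paragraph of Protocol 2.6, keep the 600 and add three things:

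1. The OTW-L number delivered at the planning limits: about 833 enrolled and about 417 completing 5 years (448 to 479 with early-SAE patients), with evaluable defined by reference to Protocol 2.7.2 and SAP 3.3.3. Label it as the yield at maximum loss and minimum enrolment, not as an expectation.
2. The loss rate or OTW-L share on which the 600 depends. The candidates are total 5-year loss of about 28% or less (up to 35.5% if early-SAE patients count), or roughly 42% to 48% of 2500 as OTW-L at 50% loss.
3. How the 600 relates to the 240 per lead, with the same statement carried into SAP 1.1.

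The cost is a few sentences of text. The downside is that the stated OTW-L size looks less favourable than 600 alone. Lowering the 600 is not proposed, since that would change a stated minimum in an FDA-required registry. If the sponsor relies on lead share, 1044 to 1200 OTW-L patients is 211 to 367 more than one third of 2500, which can be a change of mix within the same total.
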